Appendix 3 VAS for Eye Dryness

The following procedures should be followed for conducting the study assessments. The Visual Analog Scale (VAS) should be performed prior to all other ocular assessments.

To complete the VAS questionnaire, ask the subject to rate the severity and the frequency of symptom of eye dryness (0%-100%) by placing a vertical mark (|) on the horizontal line to indicate the level of eye discomfort that they are experiencing in both eyes currently (i.e., right now) and how often the eye dryness is experienced.

0% corresponds to: "no discomfort"

100% corresponds to: "maximal (the most) discomfort"

Eye Dryness Severity	0%	100%
Eye Dryness Frequency	0%	100%

Appendix 4 **OSDI**

Ocular Surface Disease Index[®] (OSDI[®])²

Ask your patients the following 12 questions, and circle the number in the box that best represents each answer. Then, fill in boxes A, B, C, D, and E according to the instructions beside each.

Have you experienced any of the following during the last week ?	All of the time	Most of the time	Half of the time	Some of the time	None of the time
1. Eyes that are sensitive to light?	4	3	2	1	0
2. Eyes that feel gritty?	4	3	2	1	0
3. Painful or sore eyes?	4	3	2	1	0
4. Blurred vision?	4	3	2	1	0
5. Poor vision?	4	3	2	1	0

Subtotal score for answers 1 to 5

(A)

(B)

(C)

(D)

Have problems with your eyes limited you in performing any of the following during the last week ?	All of the time	Most of the time	Half of the time	Some of the time	None of the time	N/A
6. Reading?	4	3	2	1	0	N/A
7. Driving at night?	4	3	2	1	0	N/A
8. Working with a computer or bank machine (ATM)?	4	3	2	1	0	N/A
9. Watching TV?	4	3	2	1	0	N/A

Subtotal score for answers 6 to 9

Have your eyes felt uncomfortable in any of the following situations during the last week ?	All of the time	Most of the time	Half of the time	Some of the time	None of the time	N/A
10. Windy conditions?	4	3	2	1	0	N/A
11. Places or areas with low humidity (very dry)?	4	3	2	1	0	N/A
12. Areas that are air conditioned?	4	3	2	1	0	N/A

Subtotal score for answers 10 to 12

Add subtotals A, B, and C to obtain D (D = sum of scores for all questions answered)

(E)

Total number of questions answered

(do not include questions answered N/A)

Please turn over the questionnaire to calculate the patient's final OSDI® score.

Evaluating the OSDI[®] Score¹

The OSDI® is assessed on a scale of 0 to 100, with higher scores representing greater disability. The index demonstrates sensitivity and specificity in distinguishing between normal subjects and patients with dry eye disease. The OSDI® is a valid and reliable instrument for measuring dry eye disease (normal, mild to moderate, and severe) and effect on vision-related function.

Assessing Your Patient's Dry Eye Disease^{1,2}

Use your answers D and E from side 1 to compare the sum of scores for all questions answered (D) and the number of questions answered (E) with the chart below.* Find where your patient's score would fall. Match the corresponding shade of red to the key below to determine whether your patient's score indicates normal mild, moderate, or severe dry eye disease.

Appendix 5 Standard Patient Evaluation of Eye Dryness (SPEED) Questionnaire

The following procedure should be followed for conducting the study assessments.

Report the type of SYMPTOMS you experience and when they occur:						
	At This Visit		Within Past 72 Hours		Within Past 3 Months	
Symptoms	Yes	No	Yes	No	Yes	No
Dryness, Grittiness, or Scratchiness						
Soreness or Irritation						
Burning or Watering						
Eye Fatigue						

Report the **FREQUENCY** of the above-checked symptoms as Never, Sometimes, Often, or Constant using the numbering system below:

Symptoms	0	1	2	3	
Dryness, Grittiness, or Scratchiness					0 = Never
Soreness or Irritation					1 = Sometimes
Burning or Watering					2 = Onen 3 = Constant
Eye Fatigue					

Report the SEVERITY of your symptoms using the rating list:						
Symptoms	0	1	2	3	4	
Dryness, Grittiness, or Scratchiness						
Soreness or Irritation						
Burning or Watering						
Eye Fatigue						
0 = No problems						

1 = Tolerable – not perfect but not uncomfortable

2 = Uncomfortable – irritating but does not interfere with my day

3 = Bothersome - irritating and interferes with my day

4 = Intolerable – unable to perform my daily tasks

Appendix 6 Corneal Fluorescein Staining (CFS) Procedure - Using NEI Scale

The procedure for evaluating corneal staining should be completed after the Tear Film Breakup Time (TBUT). If the CFS is done closely following the TBUT, then an additional application of fluorescein dye is not required. If a long time has elapsed between the TBUT and the CFS then an additional application of fluorescein dye may be required.

The process of completing the TBUT followed by the CFS may be completed right eye first followed by the left eye. A second fluorescein strip to apply dye to the left eye is required with this technique. If preferred, the TBUT followed by the CFS may be performed by alternating between the right and left eye. Starting first with the TBUT right eye, followed by TBUT left eye, then CFS right eye, then CFS left eye. Using this technique only one fluorescein strip is required to apply the dye to both the right and left eye.

- 1. Wet a sponsor supplied Fluorescein strip with the sponsor supplied saline solution/eye wash. Use enough liquid to wet the end of the strip without liquid falling from the end of the strip.
- 2. Ask the subject to look up and touch the moistened strip to the inferior palpebral conjunctiva without touching the strip to the bulbar conjunctiva.
- 3. Ask the subject to blink several times to distribute the fluorescein dye.
- 4. Wait between 2 to 3 minutes before evaluating the cornea for staining.
- 5. Use the cobalt blue illumination and the Wratten yellow filter to assess the corneal staining.
- 6. Record the staining for each of the 5 regions of the cornea, central, inferior, nasal, temporal, and superior using the NEI 0-3 scoring scale (see diagram). The CFS total score will be the sum of the five areas (0 to 15).

Grade each region, Central (1), Superior (2), Temporal (3), Nasal (4), Inferior (5), for each eye according to the following grading scale:

- 0 =No Staining
- 1 = Mild Staining
- 2 = Moderate Staining
- 3 = Severe Staining

NEI Corneal Staining Grading - Scale

Appendix 7Conjunctival Lissamine Green Staining (LGS) Procedure - Using the NEI Scale

Using this technique only one lissamine strip is required to apply the dye to both the right and left eye.

- 1. The goal is to moisten the strip without having a drop of dye ready to fall from the end of the strip. Wet a sponsor supplied Lissamine strip with the sponsor supplied saline solution/eye wash. If a drop of excess dye hangs from the end of the moistened strip, then shake off the excess over a paper towel. The moistened strip is now ready to use.
- 2. Ask the subject to look up and touch the moistened strip to the inferior palpebral conjunctiva without touching the strip to the bulbar conjunctiva.
- 3. Ask the subject to blink several times to distribute the lissamine dye.
- 4. Wait between 1 to 4 minutes before evaluating the conjunctiva for staining.
- 5. Use the moderate illumination to assess the conjunctival staining.
- 6. Record the staining for each of the 6 regions of the conjunctiva. The temporal conjunctive is divided into 3 sections, zones 1, 2, and 3, temporal, superior temporal, inferior temporal, respectively. The nasal conjunctive is divided into 3 sections, zones 4, 5, and 6, superior nasal, inferior nasal, and nasal, respectively. Grade the conjunctival staining using the NEI 0-3 scoring scale (see diagram). The LGS total score will be the sum of the six areas (0 to 18).
- 7. The staining produced by an elevated pinguecula may not improve. The staining associate with the pinguecula may be consistently excluded from the total Lissamine score.

Appendix 8Best Corrected Visual Acuity

BCVA will be conducted at all Visits.

Visual acuity testing should precede any examination requiring contact with the eye or instillation of study dyes. LogMAR visual acuity must be assessed using an ETDRS or modified ETDRS chart. Visual acuity testing should be performed with best correction using subject's own corrective lenses (spectacles only) or pinhole refraction.

An ETDRS or modified ETDRS chart may be used. If a Lighthouse chart is used (24.5" by 25"; either reflectance or retro-illuminated), the subject must view the chart from a distance of exactly 4 meters (13.1 feet). If smaller reproductions (18" by 18", e.g., Prevent Blindness) are used, the subject viewing distance should be exactly 10 feet. Reflectance wall charts should be frontally illuminated (60-watt bulb or a well-lit room).

The subject should be positioned according to the elevation of the chart (either seated or standing) so that the chart is at a comfortable viewing angle. The right eye should be tested first. The subject should attempt to read each letter, line-by-line, left to right, beginning with line 1 at the top of the chart. The subject should be told that the chart has letters only, no numbers. If the subject reads a number, he or she should be reminded that the chart contains no numbers, and the examiner should then request a letter instead of the number. The subject should be asked to read slowly, about 1 letter per second, to achieve the best identification of each letter. He/she is not to proceed to the next letter until he/she has given a definite response. If the subject changes a response before he has read aloud the next letter, then the change must be accepted.

Maximum effort should be made to identify each letter on the chart; the subject should be encouraged to guess. When it becomes evident that no further meaningful readings can be made, the examiner should stop the test. The number of letters missed or read incorrectly should be noted.

In order to provide standardized and well-controlled assessments of visual acuity during the study, consistently use the same lighting conditions throughout the study.

LogMAR Visual Acuity Calculations

After each measurement of visual acuity, the visual acuity score for the visit is calculated. The last line in which a letter is read correctly will be taken as the base logMAR reading. To this value will be added the number "N x 0.02" where 'N' represents the total number of letters missed up to and included in the last line read. This total sum represents the logMAR visual acuity for that eye.

For Example: Subject correctly reads 4 of 5 letters on the 0.2 line, and 2 of 5 letters on the 0.1 line.

Base logMAR	= 0.1
N (total number of letters incorrect on line 0.2 and line 0.1)	= 4
N x T (T=0.02)	= 0.08
Base \log MAR + (N x T)	= 0.1 + 0.08
logMAR VA	= 0.18

Appendix 9Slit Lamp Biomicroscopy and External Eye Exam Procedures

Biomicroscopy

Fluorescein dye is to be instilled into the ocular cul-de-sac, or alternatively, fluorescein strips may be used to facilitate this examination.

The physician will examine the following using their usual technique:

- Eyelids (including punctum size)
- Lashes
- Conjunctiva
- Sclera
- Cornea
- Anterior Chamber
- Iris/pupil
- Lens

Except for Eyelids (Parameters below), findings will be reported as normal, abnormal non-clinically significant, or abnormal clinically significant. For any findings of "abnormal", the Investigator will provide all relevant explanation/comment.

Eyelid/Eyelid Margin Evaluations

Eyelid Vascularity

- 0 = Normal Typical vascularity for patient age
- 1 = Mild vascular engorgement Slightly dilated and pink blood vessels involving up to 1/3 of the lid margin
- 2 = Moderate vascular engorgement Slightly more dilated pink/red blood vessels involving between 1/3 and 2/3 of the lid margin
- 3 = Severe vascular engorgement Multiple significantly dilated red blood vessels involving between 1/3 and 2/3 of the lid margin
- 4 = Very Severe vascular engorgement Multiple significantly dilated deep red blood vessels involving >2/3 of the lid margin

Meibomian glands (Out of 10 glands evaluated for the lower and upper eyelids)

- 1 = Normal: Clear orifices of meibomian glands
- 2 = Mild: Less than 1/3 of orifices plugged
- 3 = Moderate: Between 1/3 and 2/3 of orifices plugged
- 4 = Severe: More than 2/3 of orifices plugged
- 5 = Very severe: All orifices plugged

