8.3 Study Assessments by Visit

For every visit, perform study procedures as referenced in the Schedule of Events (Appendix 1) in the order specified below in both eyes. Note: Procedures will apply to both Cohort 1 and Cohort 2 unless otherwise indicated. An asterisk (*) indicates the assessment may occur at any time during the visit.

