8.3.4 Follow-Up Visit 3 (Week 2 ±2 days)

- Record concomitant medications *
- Record AEs *
- Collect and review Subject Daily Diary for Artificial Tear Use (as needed) *
- VAS for Eye Dryness
- OSDI
- SPEED assessment
- BCVA assessment
- Slit lamp biomicroscopy, including punctum assessment
- OTX-CSI or HV Insert Presence by visual Assessment
- Ease of Visualization by Investigator (Appendix 14)
- Corneal fluorescein staining (NEI scale)
- Conjunctival Lissamine Green Staining (NEI scale)
- Systemic PK (at selected sites)

Note: Wait 20 minutes prior to conducting Schirmer/Tear Film PK

- Schirmer Test (without anesthesia) and Tear Film PK
- Dispense artificial tears (as needed)
- Dispense Daily Subject Diary for Artificial Tear Use (as needed)

Note: All ophthalmic assessments must be performed on both eyes.

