8.3.8 Follow-Up Visit 7 (Week 12 ±3 days)

- Record concomitant medications *
- Record AEs *
- Collect and review Subject Daily Diary for Artificial Tear Use (as needed) *
- VAS for Eye Dryness
- OSDI
- SPEED assessment
- BCVA assessment
- Slit lamp biomicroscopy, including punctum assessment
- OTX-CSI or HV Insert Presence by visual Assessment
- Ease of Visualization by Investigator
- TBUT
- Corneal fluorescein staining (NEI scale)
- Conjunctival Lissamine Green Staining (NEI scale)
- Schirmer Test (without anesthesia) and Tear Film PK Note: Wait 20 minutes prior to conducting Schirmer/Tear Film PK
- Dispense artificial tears (as needed)
- Dispense Daily Subject Diary for Artificial Tear Use (as needed)

Note: All ophthalmic assessments must be performed on both eyes.

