Appendix 14 OTX-CSI or HV Insert Ease of Visualization

The Investigator will assess the presence of an OTX-CSI or HV insert at each study visit, using a blue light and yellow filter. The Investigator will be asked to grade the level of ease of visualization of the punctum plug as "easy", "moderate", or "difficult".

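### At every follow-up visit the set order puts the fluorescein step directly before the insert check, which uses fluorescein-viewing optics; presence could be misread, and recording it before any dye costs nothing

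*Protocol*

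**What the plan says.** Protocol Section 8.3 tells sites to "perform study procedures as referenced in the Schedule of Events (Appendix 1) in the order specified below in both eyes". The only exception is for marked items: "An asterisk (*) indicates the assessment may occur at any time during the visit". Neither biomicroscopy nor the insert check carries an asterisk at any follow-up visit.

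From 8.3.4 (Week 2) to 8.3.10 (the 30-day visits) the same run of lines appears: "Slit lamp biomicroscopy, including punctum assessment", then "OTX-CSI or HV Insert Presence by visual Assessment", then ease of visualization, then tear film break-up time (Weeks 6 and 12 only), then corneal fluorescein staining.

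Three appendices describe the dye and the optics:
- Appendix 9, biomicroscopy: "Fluorescein dye is to be instilled into the ocular cul-de-sac, or alternatively, fluorescein strips may be used to facilitate this examination". Both options are fluorescein.
- Appendix 14, insert check: "The Investigator will assess the presence of an OTX-CSI or HV insert at each study visit, using a blue light and yellow filter". Appendix 13 describes the same light and filter and places the insert just below the punctal opening.
- Appendix 6, corneal staining: "Use the cobalt blue illumination and the Wratten yellow filter to assess the corneal staining".

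The 20-minute wait in the visit lists applies only to the Schirmer test and tear film sampling.

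**The concern.** A site that follows the protocol exactly looks for the insert straight after the step that calls for fluorescein, with the kind of light and filter that shows fluorescein. The dye goes into the tears, and the insert sits just inside the opening through which tears drain. Dye left at the punctum might be taken for an insert that has gone, or might make a true insert harder to pick out.

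Elsewhere the protocol does attend to dye order. Appendix 8 puts visual acuity before any study dye, and the break-up time and staining dye already comes after the insert check. Only the Appendix 9 dye falls on the wrong side of it.

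Visual presence is the trial's direct measure of retention. It feeds:
- the exploratory presence and ease-of-visualization endpoints, and their tests of each OTX-CSI formulation and pooled OTX-CSI against each vehicle (SAP 4.7.4);
- exposure duration (SAP 4.6);
- the Week 16 choice between exit and return every 30 days (Protocol 6.1);
- the replacement rule for the roughly 5 subjects in Cohort 1 (Protocol 8.3.11).

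**Working it through.** The plan states no detection error rate and no power, so there is no figure of its own to reproduce. The check has two parts.

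**1. Sequence.** The visit lists for Weeks 2, 4, 6, 9, 12, 16 and the 30-day visits all place biomicroscopy one line above insert presence. Set beside Appendices 6, 9, 13 and 14, this confirms the order and the shared type of optics. Nothing in either document inserts a rinse, a wait or a pre-dye look.

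**2. Size, for illustration.** Let p be true presence in an arm, f the share of empty eyes read as present, and m the share of true inserts missed. Assume f and m are the same in all arms.

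- Observed presence = p(1-m) + (1-p)f.
- Difference between arms A and B = (pA - pB)(1 - m - f).
- Error in the level of presence = (1-p)f - pm.

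With m = 0, differences are multiplied by (1-f) and presence is overstated. With m above 0, differences shrink further, but the level can err in either direction.

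Arm sizes of 40, 40, 40 and 20 are from Protocol Table 2. The true presence rates and f are assumptions. Power is for the planned two-sided Fisher test at 0.05, summing the binomial probabilities of all tables with p ≤ 0.05. A normal approximation agrees to within 0.07.

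| Planned contrast, assumed truth | f | Observed | Difference | Power |
|---|---|---|---|---|
| One OTX-CSI arm 30% vs F3 0% (40 vs 20) | 0 | 30% vs 0% | 30 | 0.945 |
| | 5% | 33.5% vs 5% | 28.5 | 0.741 |
| | 10% | 37% vs 10% | 27 | 0.583 |
| | 20% | 44% vs 20% | 24 | 0.393 |
| F1 30% vs F2B 60% (40 vs 40) | 0 | 30% vs 60% | -30 | 0.725 |
| | 10% | 37% vs 64% | -27 | 0.622 |
| | 20% | 44% vs 68% | -24 | 0.513 |
| One OTX-CSI arm 90% vs F3 0% (40 vs 20) | 0 | 90% vs 0% | 90 | about 1.0 |
| | 20% | 92% vs 20% | 72 | about 1.0 |

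*Formulation 3.* It is designed to last about 1 week. If none remains at Week 2, the 20 study eyes give 20f false readings: 0.4, 1, 2 or 4 at f = 2%, 5%, 10% or 20%. The chance of at least one is 1-(1-f)^20: 33%, 64%, 88% or 99%.

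*Week 16.* With both inserts gone and eyes treated as independent, the chance of at least one false reading is 1-(1-f)^2: 4%, 10%, 19% or 36%.

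*Exposure.* SAP 4.6 counts to the latest date on which absence is confirmed. Read literally, a false reading at an intermediate visit followed by a confirmed absence changes nothing. If the first confirmed absence is meant, a false reading at that visit moves the date by one interval: 2, 2, 3, 3 or 4 weeks between Weeks 2, 4, 6, 9, 12 and 16. For subjects who leave before both inserts have gone, the end date is the last visualization, which a false reading can push later. In every case an error in one eye has no effect while the other eye still holds its insert.

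**The case against.** The strongest reply is that no harm is shown. Neither document says dye is mistaken for an insert, gives an error rate, or explains why the insert shows under blue light. The insert is a discrete body 2.7 mm long below the punctal opening (Protocol 4.3 and Appendix 13), and Appendix 15 has it identified through the punctal tissue. An experienced examiner may tell it from dye without difficulty. Appendix 9 also leaves the examination to the physician's usual technique and does not say when within it the dye goes in. All of this stands, so f may be near zero.

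Some errors would also show in the data. Cohort 2 inserts are not replaced, so a record of absent followed by present in the same eye is contradictory. That check misses a false reading made before any absence is recorded. Tear film drug levels give indirect support, but only in the active arms.

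A reader might infer several stronger things that the documents do not support:
- That retention is in fact mis-measured. Only a risk of misreading follows from the text.
- That the F1 versus F2A comparison is diluted. Protocol 4.2 names that comparison, but SAP Section 5 drops it and takes precedence.
- That each false reading adds a visit interval to exposure. SAP 4.6 does not work that way in general.
- That a false reading at Week 16 forces continued follow-up. Protocol 6.1 lets the investigator exit a subject at any time.

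**Conclusion.** The sequence problem is confirmed at every scheduled follow-up visit. Its effect is possible but not demonstrated. With an equal f across arms and no missed inserts, presence is overstated and planned OTX-CSI versus vehicle differences shrink by (1-f). Moderate contrasts would lose power at an f of 10% to 20%, while very large ones would still be detected. If dye also hides true inserts, the direction of error in the level of presence is open. Exposure duration and the 30-day return can be affected, but neither automatically.

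Severity is minor. The affected endpoints are exploratory and the primary Schirmer analysis does not use insert presence. The case for acting is that the risk is avoidable at no cost.

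**What to change.** In Protocol 8.3.4 to 8.3.10, list insert presence and ease of visualization before slit lamp biomicroscopy. Alternatively, leave the lists as they are and state in Appendices 9 and 14 that no fluorescein is instilled until both have been recorded. The rest of the order stays the same.

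The cost is two lines moved in each visit list, or one sentence in each of two appendices. No procedure, visit time, staff or equipment is added, since Appendix 13 already allows either a slit lamp or a hand-held blue light.

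If visits are already complete, the study report should state the order sites actually used, note the possible misreading beside the presence and exposure tables, and list any Cohort 2 eye recorded absent and later present.

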Appendix 10 PK Sample collection (Systemic and Tear Film Sample)

Systemic PK

Refer to laboratory manual for complete procedure.

Tear Film PK Sample

Tear fluid samples will be collected from both eyes at the same time.

Refer to the lab procedure manual for the complete procedure.

Appendix 11 Tear Film Break-Up Time

The time required for the tear film to break up following a blink is called TBUT. It is a quantitative test for measurement of tear film stability. The normal time for tear film breakup is over 15 seconds. A fluorescein strip is moistened with saline and applied to the inferior cul-de-sac. After a couple of blinks, the tear film is examined using a broad-beam of slit lamp with a blue filter for the appearance of the first dry spots on the cornea. TBUT values of less than 5–10 seconds indicate tear instability and are observed in patients with mild to moderate dry eye disease.

